## 1) Objectives

- Aim 1: Evaluate the efficacy of 4 weeks of daily BWL exposure in reducing PTBIF immediately post-treatment and at one-month follow-up.
  - H1: Individuals receiving 4 weeks of daily BWL treatment will report significant reductions in fatigue compared to those receiving DRL
  - H2: Treatment effects will be maintained one month after treatment completion
- Aim 2: Explore potential effects of BWL exposure on mood, sleepiness, sleep quality, circadian rhythms, anxiety, cognition and life satisfaction.
  - H3: Individuals receiving 4 weeks of daily BWL treatment will report significant reductions in daytime sleepiness and depressed mood as well as improvements in sleep quality and circadian rhythms, compared to those receiving DRL
  - RQ1: Is treatment with BWL associated with improvements in anxiety, cognition and life satisfaction?
- Aim 3: Investigate potential mechanisms for effects of BWL exposure on fatigue, including changes in mood, sleepiness, sleep quality and circadian rhythms.
  - RQ2: Are treatment-related changes in fatigue mediated or moderated by mood, sleepiness, sleep quality and circadian rhythms?
- Aim 4: Determine whether individual characteristics are associated with treatment outcomes.
  - RQ3: Are demographic or other patient characteristics associated with positive treatment outcomes?

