research is under way in Australia examining the effects of blue light, with some positive preliminary results. We have chosen to examine the benefits of BWL rather than blue light in the proposed study for two reasons. First, evidence suggests that extended exposure to blue light may have harmful effects on the retina in older adults. Second, there is strong evidence that as people age, their circadian photoreception decreases, particularly for blue light. Using full spectrum BWL (400nm to 740nm) maximizes the potential benefits of light therapy in adults over 50, who represent a large and growing proportion of people with TBI. In the proposed study, we will examine the effects of age on therapy outcomes. Light therapy also has potential for PTBIF because of its low cost (less than \$200 for a Litebook), apparent lack of side effects and ease of access (it can be easily used at home without supervision), making it safer and more attractive for treating fatigue than pharmacological treatments.

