### b. Data Analyses: Overview

We will calculate descriptive statistics for all measures. We will examine distributions and address substantial non-normality using data transformations, as necessary. If we detect a significant baseline group imbalance on a demographic or clinical variable, we will include that variable as a covariate in subsequent analyses. Dropouts and treatment completers will be compared on baseline variables. We will examine associations among demographic characteristics and outcome measures to identify necessary covariates for subsequent analyses.

We will fit random effects models to test the primary hypotheses, examining the effects of treatment over time. This model is a preferable alternative to traditional repeated measures ANOVA or ANCOVA, in that it takes into account the correlated nature of repeated measurement within an individual. The model allows us to examine the influence of demographic and injury characteristics prior to the inclusion of the treatment effect. We will conduct analyses on the full Intent-To-Treat sample (all subjects randomized) using full maximum likelihood estimation. We will determine model fit using Akaike's Information Criteria.

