*RQ1: We will assess whether treatment with BWL is associated with changes in circadian rhythms and improvements in anxiety, cognition and life satisfaction using the analyses described for H1, with Neuro-QOL Anxiety, CNS Vital Signs Neurocognitive Index and CFQ (cognition), and SWLS (life satisfaction) as the respective dependent variables.*

*RQ2: As it is not clear whether BWL's effects on PTBIF are direct effects or secondary to changes in other domains, we will examine whether PTBIF scores are mediated or moderated by mood, sleepiness, sleep quality and circadian rhythms. These analyses will focus on the magnitude of the effect, as recommended by Kraemer et al. We will use a fixed-effects approach in which the dependent variable is the GFI pre-post change. We will compare the between treatment group effect sizes for those with and without the respective potential mediator or moderator. An effect will be considered present if a substantial difference in effect size is observed. Results from these exploratory analyses could be used to guide the design of future RCTs that would focus on those subjects most likely to respond to BWL.*

*RQ3: Because current research suggests that age, gender and injury severity may be associated with treatment outcome, we will examine these individual characteristics and any others that the literature suggests may be relevant at the time of analysis. We will add these variables to the multilevel model one at a time and test to determine if the variable improves fit. Continuous variables that improve the fit will be examined further by determining the correlation between them and GFI separately for the two treatment groups, and comparing the strength of the correlations.*

e. Statistical Power

[The sample size for this study will provide adequate power to test the primary hypothesis. We will recruit enough subjects to fill the Treatment (DRL-BWL)-by-Time (pre-post) repeated measures design (40 subjects per treatment group, total N = 80). This design achieves 90% power to test the treatment effect using a Geisser-Greenhouse Corrected F Test with a 5% significance level, based on an effect size of 0.37, and achieves 81% power to test the Treatment-by-Time interaction using a Geisser-Greenhouse

	Protocol Name:	Management of post-TBI fatigue with light exposure
	Principal Investigator:	[name]., ABPP/Cn

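### RQ3 screens each patient characteristic on its own contribution to model fit and names no characteristic-by-treatment-by-time term; its only by-arm look is informal and limited to continuous variables that pass

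*Combined protocol and SAP*

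**What the plan says.** Aim 4 (section 1, RQ3) asks: "Are demographic or other patient characteristics associated with positive treatment outcomes". The Background adds, on age, that "we will examine the effects of age on therapy outcomes".

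Section 6.d gives the method for RQ3. It names three characteristics on the ground that "age, gender and injury severity may be associated with treatment outcome", and leaves room for others chosen when the analysis is done. There are two steps:

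- Step 1, the gate: "We will add these variables to the multilevel model one at a time and test to determine if the variable improves fit". The criterion comes from section 6.b: "We will determine model fit using Akaike's Information Criteria".
- Step 2, only for variables that pass and are continuous: "Continuous variables that improve the fit will be examined further by determining the correlation between them and GFI separately for the two treatment groups", ending in "comparing the strength of the correlations".

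No product of a characteristic with treatment, or with treatment and time, appears in RQ3 or elsewhere in section 6. Step 2 gives no test, no threshold, and no indication whether GFI means T2, T3 or change from T1.

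RQ2, the paragraph before, treats its moderators differently. It takes GFI pre-post change as the outcome and says: "We will compare the between treatment group effect sizes for those with and without the respective potential mediator or moderator". That covers mood, sleepiness, sleep quality and circadian rhythms, not age, gender or injury severity.

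**The concern.** A covariate entered alone in a repeated-measures model that includes the pre-treatment visit is judged by its association with fatigue averaged over visits and arms. A characteristic that changes the BWL effect can have little or no such average association, and then it is dropped before anyone looks at it by arm. A characteristic that only marks people who are always more fatigued passes easily.

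Categorical characteristics stop at step 1. Gender is named in RQ3 but never compared between arms; the same holds for injury severity if it is analysed in categories.

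At stake is the answer to Aim 4. The trial could report that no characteristic is linked to response largely because the screen removed the candidates. Or it could report a characteristic that passed step 1 as if it predicted response.

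**Working it through.** **The plan's own figures.** No power is stated for RQ3. Those stated for the primary design reproduce with the effect sizes read as Cohen's f and N = 80: noncentrality 80 × 0.37² = 10.95 gives 90.5% (stated 90%), and 80 × 0.32² = 8.19 gives 80.7% (stated 81%). So N = 80, 40 per arm, is a sound basis for the check.

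**Assumptions not in the documents.** A continuous characteristic X in SD units; GFI residual SD 1 at each visit; T1-T2 correlation ρ = 0.5, with 0.7 as a second value; modifier slopes in SD of GFI per SD of X, acting at T2 only; step 2 tested by Fisher z at 5% on T2 GFI. One added parameter improves AIC when the likelihood-ratio statistic exceeds 2, that is |z| > √2 = 1.414.

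**Step 1 by hand, ρ = 0.5.** The residual SD of a subject's two-visit mean is √((1 + 0.5)/2) = 0.866.

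- Noise: P(|Z| > 1.414) = 16% in large samples, about 17% simulated.
- Slope −0.5 under BWL only: the slope on the two-visit mean is −0.25 under BWL and 0 under dim red light (DRL), pooled −0.125. Then |z| = 0.125/0.866 × √80 = 1.29, and the pass rate is about 45%.
- Equal and opposite slopes: the pooled slope is 0, so the pass rate is about that of noise.
- Prognostic only, 0.4 at both visits: z = 0.4/0.866 × √80 = 4.13, and the pass rate is above 99%.

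**Direct interaction test by hand, ρ = 0.5.** The residual variance of change is 2(1 − 0.5) = 1. The standard error of the slope difference is √(1/40 + 1/40) = 0.224. For a difference of 0.5, z = 2.24 and normal-approximation power is 61%; simulation with sampled X and a t reference gives about 57%.

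**Simulation, ρ = 0.5** (thousands of trials per scenario; ranges are the spread between runs):

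| Scenario | Passes AIC gate | Gate plus step 2 | Step 2 without gate | Direct interaction |
|---|---|---|---|---|
| No association | 17% | 1% | 5% | 5% |
| Prognostic only, 0.4 | 99% | 5% | 5% | 5% |
| BWL only, 0.5 | 45% | 25% | 56% | 57% |
| Crossing, ±0.25 | 17% | 9-10% | 57-58% | 57-59% |
| Crossing, ±0.4 | 17-18% | 16-17% | 92-93% | 92% |

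**Sensitivity.** With ρ = 0.7 the BWL-only 0.5 modifier is found in 24% by the plan's path and 78% by the direct test; for the ±0.4 crossing modifier it is 16% and 99%. A stronger BWL-only slope of 0.64 at ρ = 0.5 gives 43% against 78%. A characteristic with both a prognostic slope of 0.3 and a BWL slope of −0.6 gives 41% against 73%. The gap narrows with stronger effects but does not close.

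**Where the loss arises.** At ρ = 0.5, ungated step 2 performs almost as well as the interaction test. The gate causes the loss.

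**The case against.** A reader might infer that RQ3 never examines characteristic-by-treatment effects. The documents do not support that: the sentence after the gate compares arm-specific correlations, which is a by-treatment look. The statement is true only for categorical variables.

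A reader might also infer that prognostic variables will be reported as modifiers. For continuous variables that does not follow. About 99% pass the gate, but if step 2 is formally tested only about 5% are labelled modifiers, the same as under a direct interaction test. Aim 4 is also worded loosely enough to include prognosis, so flagging such a variable is an error only if it is presented as predicting response to BWL.

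A gate run at p < 0.05 would look worse: about 23% pass and 12-13% detected for the BWL-only 0.5 modifier. Section 6.b names AIC, so the AIC figures are the right ones.

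Two points of reading remain. Section 6.c speaks of adding the treatment effect in order to see an effect over time, so adding a variable might include its product with time. The text does not say so, and a main effect is the plainer reading. Nor can one say that step 2 uses GFI level instead of change; the text is silent. At ρ = 0.5 this makes little difference, since the modifier slope is 0.5 and the residual variance is 1 on either scale.

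Finally, RQ3 is exploratory, carries no hypothesis and no power claim, and the exact crossing pattern is the least favourable case for the gate. All of that stands and limits the weight of the point. It does not justify a screen that removes the variables the aim is looking for.

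**Conclusion.** The point holds in a limited form. RQ3 gates on a variable's own contribution to fit, specifies no characteristic-by-treatment-by-time term, and confines its by-arm look to an unspecified comparison of correlations for continuous variables that pass. Under the assumed inputs the plan's path has less than half the detection rate of a direct test for a BWL-only 0.5 SD modifier (25/57 = 0.44), and about a sixth for crossing modifiers (10/57 and 16/92 are both near 0.17).

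These sizes rest on assumed slopes and T1-T2 correlations, on 80 completers, on the main-effect reading of step 1, and on a formal test in step 2 that the plan does not state. That gender has no by-arm step depends on none of these. The primary analysis and H1-H3 are not affected. This should be changed, but it does not threaten the trial's main conclusion.

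**What to change.** In section 6.d, RQ3:

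- Remove the fit gate and the correlation comparison.
- For each of age, gender and injury severity, fit the GFI model with characteristic × treatment × time and all lower-order terms, or equivalently simple, characteristic × treatment on GFI change. State how injury severity is coded and which visits enter.
- Report each interaction with a 95% confidence interval, labelled exploratory, whatever the result.
- If prognosis is also wanted, report characteristic × time separately under that name.
- Label any characteristic added later as post hoc.

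The cost is a change of SAP wording and three model fits, with no new data. The downside is wide intervals at N = 80, which is acceptable for an exploratory aim and shows honestly how little the trial can say about modifiers.

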*Treatment effects.* Change scores were used for between-group comparisons to remove effects of any baseline differences between groups. Robust effect sizes in Cohen’s “medium” and “large” ranges were seen for BWL both between and within groups (0.32-1.56) on fatigue measures (see Appendix VI for all effect sizes). In most cases, effects were somewhat decreased at follow up but were generally in the medium range. This is unexpected, as past research indicates that treatment effects dissipate after treatment is discontinued. Medium or larger effect sizes were also noted for BWL on measures of daytime sleepiness, sleep quality and mood. Effect sizes for DRL were generally small.

Actigraphy findings indicated improvements in sleep in both groups but with larger effect sizes for BWL. Circadian rhythm data were more ambiguous, with modest changes in phase and rhythmicity in both groups. These findings suggest that BWL and DRL therapy are safe, feasible and credible for use with individuals with TBI, that the measures selected were sensitive to treatment effects and that BWL may be a promising treatment for PTBIF, with potential benefits for daytime sleepiness, mood, circadian rhythms and sleep as well. Indeed, daytime sleepiness, mood, circadian rhythms, and sleep quality may actually function as mediators or moderators of BWL treatment effects on PTBIF, given their documented responsiveness to light exposure. Because of the promising initial findings in our small pilot study and the need for empirically validated PTBIF treatment, an *Intervention Efficacy* trial investigating the effect of BWL on PTBIF is warranted. Based on: 1] the literature on alerting effects and cognitive benefits of BWL and the connection between PTBIF and cognition; 2] our own unpublished research suggesting the important role of anxiety in PTBIF and sleep disturbance; and 3] potential improvements in life satisfaction resulting from BWL effects on function, we will evaluate cognition, anxiety and life satisfaction as potential secondary effects of treatment.

To date, no trials of BWL treatment have been conducted in individuals with TBI. However,

	Protocol Name:	Management of post-TBI fatigue with light exposure
	Principal Investigator:	[name]., ABPP/Cn
	Primary Contact Name/Contact Info:	[name], [contact] , [name]
	Date Revised:	3/9/2016
	Study Number:	IF1813452

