### c. Hypothesis Testing

*H1: Individuals receiving daily BWL treatment will report significant reductions in fatigue from baseline compared to those receiving DRL.* The primary outcome measure, GFI, will be the dependent variable in the multi-level regression. We will enter time into the model first and examine fit. We will add any demographic or study measures identified as potential confounders in the preliminary analyses, and examine improvement of fit. Finally, we will add the treatment effect to the model and examine differences in fit to determine the presence and strength of the treatment effect over time. The same analyses will be conducted using our secondary fatigue outcome measure, the TBI-QOL Fatigue.

	Protocol Name:	Management of post-TBI fatigue with light exposure
	Principal Investigator:	[name]., ABPP/Cn
	Primary Contact Name/Contact Info:	[name], [contact] , [name]
	Date Revised:	3/9/16
	Study Number:	IF1556212

*H2: Individuals receiving daily BWL treatment will report significant reductions in daytime sleepiness and depressed mood as well as improvements in sleep quality and circadian rhythms from baseline compared to those receiving DRL.* Testing of this hypothesis will be identical to that for H1, with ESS (sleepiness), Neuro-QOL Depression (mood), NeuroQol Sleep (sleep quality) and circadian rhythm measures (from Actigraphy) as the dependent variables.

*H3: Treatment effects will be maintained one month after treatment completion.* Pilot data suggests that the positive effects of BWL persist beyond termination of active treatment. To address whether treatment effects are indeed maintained one month after treatment completion, we will extend the multilevel analysis for H1 to include data from the T3 follow-up assessment. One advantage of a third assessment is that the possibility of time as a non-linear effect can be explored. Model fit for a linear versus non-linear time effect will be compared to determine best fit. As in H1, any demographic or study measures identified in the preliminary analyses will be added, with examination of improvement of fit. Finally, we will add the treatment effect to the model to examine the persistence of the treatment effect over time.

d. Research Questions

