	Primary Contact Name/Contact Info:	[name], [contact] , [name]
	Date Revised:	3/9/16
	Study Number:	IF1556212

Corrected F Test with a 5% significance level, based on an effect size of 0.32. Effect sizes (Appendix VI) were chosen based on the pilot findings, and then reduced by 20% to correct for possible inflation given the small sample size. []

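### The power section gives 90% for a treatment effect and 81% for Treatment-by-Time without saying which applies to H1; H1 is the Treatment-by-Time contrast, so the plan's own figure for it is 81%

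*Combined protocol and SAP*

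**What the plan says.** Section 6.e opens with a general assurance: "The sample size for this study will provide adequate power to test the primary hypothesis". It describes a two-arm, pre-post repeated-measures design with 40 subjects per arm (80 in total; the Number of Subjects section makes clear that these are completers). Two powers follow. The first is "This design achieves 90% power to test the treatment effect using a Geisser-Greenhouse Corrected F Test with a 5% significance level", at an effect size of 0.37. The second says that the design "achieves 81% power to test the Treatment-by-Time interaction", at an effect size of 0.32. Both effect sizes are pilot values reduced by 20%, with a reference to Appendix VI, which is not part of the available text. The effect-size metric is not named.

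Section 6.c states H1 for the primary outcome, GFI: participants on bright white light "will report significant reductions in fatigue from baseline compared to those receiving DRL". The model is built in steps: time first, then covariates, and last "we will add the treatment effect to the model and examine differences in fit". That sentence goes on to describe the result as a treatment effect over time. Section 6.b says that fit is judged by Akaike's criterion and that all randomised subjects are analysed.

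Two other places treat fatigue as change. In the RQ2 analysis in 6.d, "the dependent variable is the GFI pre-post change". For the pilot, the Background says: "Change scores were used for between-group comparisons to remove effects of any baseline differences between groups".

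**The concern.** A reader looking for the power of the primary test meets 90% first, attached to the words *treatment effect*. Section 6.c uses the same words for the step that tests H1. The natural match is therefore 90% to H1, although H1 as worded is the contrast to which 6.e gives 81%.

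Two things are at stake. One is reporting: the assurance quoted for the primary hypothesis could be taken as 90% when the plan supports 81%. The other is analysis: an analyst who takes the last step of 6.c literally could add only a treatment main effect. In a pre-post model that term is a diluted test of H1, because half of what it averages was measured before treatment was assigned.

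**Working it through.** **Inputs.** From 6.e: 40 per arm, N = 80, 5% F test, two visits (pre, post), effect sizes 0.37 and 0.32. From Enrollment and Assessments: the baseline battery (T1) precedes randomisation. The T1-T2 correlation of GFI (rho) is not in the documents; 0.3, 0.5 and 0.7 are assumed to show a range.

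**1. Reproduce the stated powers.** With two visits the Geisser-Greenhouse epsilon is 1, so the correction changes nothing. Power comes from the noncentral F with 1 and 78 degrees of freedom and lambda = N × f².

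- f = 0.37: lambda = 80 × 0.1369 = 10.95, power 90.5% (stated 90%).
- f = 0.32: lambda = 80 × 0.1024 = 8.19, power 80.7% (stated 81%).

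Read as Cohen's d, lambda = N × d²/4 gives only 37% and 29%. Cohen's f on each tested contrast is therefore inferred, because it reproduces both figures.

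**2. Which term is H1?** Let D1 and D2 be the arm differences in mean GFI at T1 and T2.

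- Difference in change from baseline: D2 − D1. This is the Treatment-by-Time term.
- Treatment main effect: (D1 + D2)/2.

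H1 is worded as reduction from baseline compared between arms, which is D2 − D1. The reference to an effect over time in 6.c, the change score in RQ2 and the pilot's change-score comparisons agree. The plan's figure for this term is 81%.

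**3. What would the main effect deliver?** Randomisation gives D1 = 0 in expectation. With a common SD s at each visit:

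- interaction: mean D2, variance of a subject's change 2s²(1 − rho);
- main effect: mean D2/2, variance of a subject's average s²(1 + rho)/2.

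Hence f_main = f_int × √[(1 − rho)/(1 + rho)]. With f_int = 0.32:

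| rho (assumed) | f_main | Power |
|---|---|---|
| 0.3 | 0.235 | 55% |
| 0.5 | 0.185 | 37% |
| 0.7 | 0.134 | 22% |

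So 90% is not supported for a T1/T2-averaged treatment term beside an interaction of 0.32, unless 0.37 is defined in some other way.

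**4. What does a common baseline mean add?** Constraining the T1 mean to be equal across arms reduces the relevant variance from 2s²(1 − rho) to s²(1 − rho²). The effective size becomes f = 0.32 × √[2/(1 + rho)]:

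| rho (assumed) | f | Power |
|---|---|---|
| 0.3 | 0.397 | 94% |
| 0.5 | 0.370 | 90% |
| 0.7 | 0.347 | 87% |

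As rho approaches 1 the power falls towards 80.7%, so 81% is conservative for this model.

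**The case against.** The strongest reply is that nothing stated is wrong. Each power is labelled by its term, both reproduce, and 6.e never calls 90% the power for the primary hypothesis. Its claim of adequate power is met at 81% as well as at 90%. Section 6.c also does not stop at adding a treatment effect; it continues with *over time*, which points to the interaction. All of this stands. The fault is a missing link between test and power, together with one label used for two terms.

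The 0.37 may also have a sound origin. It might be the arm difference at T2 only. Under randomisation the expected T2 difference equals the expected difference in change, so that comparison would be a valid test of the same quantity, and 90% could then be its power. The 0.37 might instead come from another measure, since the pilot reported effects on several fatigue measures. Without Appendix VI neither can be ruled out, so the documents do not show that 90% is wrong on every reading. They do show that it is undefined, and that in the pre-post design that 6.e names it is not the change contrast.

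A third objection is that 81% is not exactly the power of the planned analysis either. It belongs to a repeated-measures F test in 80 completers, whereas 6.b and 6.c describe a multilevel model on all randomised subjects, with covariates chosen from the data and fit judged by Akaike's criterion. This is correct, and the fix has to address it.

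A reader might infer that the trial is underpowered or needs more subjects. Having 90% power at f = 0.32 would take 53 per arm (106 completers; 106/0.85, rounded up, is 125 enrolled). But the plan does not promise 90% for H1, so this is no shortfall against its own target.

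**Conclusion.** The point holds as one of labelling and test specification. Section 6.e does not say which power belongs to H1. On H1's own wording it is 81% (recomputed 80.7%), not the 90% given first. That rests on reading the effect sizes as Cohen's f and on 80 completers.

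If the last step of 6.c were fitted as a main effect, power for the 0.32 effect would drop to roughly 55%, 37% or 22% at the assumed correlations, given equal T1 means and equal variances. This is the practical reason to name the term. The documents do not support any claim of an arithmetic error, of an underpowered trial or of a need to enlarge it. The change should be made, but it does not put the design in doubt.

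**What to change.** **(a) Section 6.e.** State: *Power for H1 is 81%, for the Treatment-by-Time contrast in GFI (T1 to T2), effect size 0.32, repeated-measures F test at 5%, 80 completers.* Name the effect-size metric. Drop the 0.37 and its 90%, or define them (visits, measure, SD) and do not present them as the power for H1.

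**(b) Section 6.c, H1.** State that H1 is tested at two-sided 5% by the difference between arms in GFI change from T1 to T2, estimated in the multilevel model with the T1 mean constrained equal across arms. Say that the test is neither a treatment main effect nor a comparison of Akaike values. Randomisation after T1 justifies the constraint, and the T1 GFI it uses is already collected.

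**(c) Link the two sections.** Note that 81% is approximate for the intention-to-treat multilevel model and conservative under the constraint. Quote a higher power only with its assumed correlation (about 94%, 90% or 87% at 0.3, 0.5 or 0.7).

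**Cost.** Wording in two sections, one change to the planned model (the baseline constraint), and a less favourable leading power figure. Sample size, recruitment and data collection stay as they are.
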